Kidney function	 Non-adverse increased urinary glucose concentration was seen in female monkeys and rats given ≥10 mg/kg/day. Other clinical pathology that may be related to perturbations in kidney function were seen in monkeys or rats. Monkeys given ≥3 mg/kg/day for 6 weeks had decreased plasma albumin; rats given ≥10 mg/kg/day for 6 weeks had decreased urinary volume, lower urinary total protein and protein concentrations, variable changes in plasma creatinine concentration and urea, higher glucose and phosphorus concentrations and slightly lower sodium, 	 Participant Selection / Monitoring/ Stopping Criteria: Specific eligibility - criteria (see Section 6.2). The protocol includes laboratory assessments for renal function, electrolytes, fasting glucose, as well as urinary glucose assessment. Relevant renal and glycaemic safety data from the current and any previous cohort will be considered as part of dose escalation decisions.

Potential Risk of Clinical Significance	Summary of Data / Rationale for Risk	Mitigation Strategy
	 potassium and chloride concentrations. No histological changes were seen in the kidneys of monkeys given GSK3358699. Tubular dilatation and higher kidney weight was evident at the non-tolerated 100 mg/kg/day dose in male rats. Some of the urinary effects in rats are evident below the maximum predicted human exposure (AUC) at 45 mg and the NOEL in monkeys at or below parity to the maximum predicted human exposure (AUC) at 45 mg. 	

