10.4.1. Safety Analyses

All safety analyses will be performed on the Safety Population.

Endpoint	Statistical Analysis Methods	
Primary	Will be presented in tabular and/or graphical format and summarised descriptively according to GSK's Integrated Data Standards Library standards.	

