12.2. Appendix 2: Clinical Laboratory Tests

- The tests detailed in Table 6 will be performed by the local laboratory.
- Protocol-specific requirements for inclusion or exclusion of participants are detailed in Section 6 of the protocol.
- Additional tests may be performed at any time during the study as determined necessary by the investigator or required by local regulations.

Table 6	Protocol-Required Safety Laboratory Assessments

elet Count C Count moglobin matocrit od Urea ogen (BUN)	Pota	RBC Indices: MCV MCH %Reticulocytes	Aspartate	Diffe Neut Lymp Mone Eosi	C count with rential: trophils phocytes ocytes nophils ophils Total and
C Count moglobin matocrit od Urea	Pota	MCV MCH %Reticulocytes		Diffe Neut Lymp Mone Eosi	rential: trophils phocytes ocytes nophils ophils
	Pota	assium			Total and
	Pota	assium			Total and
			Aminotransfer (AST)/ Serum Glutamic- Oxaloacetic Transaminase (SGOT)	1	direct bilirubin
atinine	Sod	lium	(ALT)/ Serum Glutamic-Pyru	n uvic	Total Protein
	-		Cholesterol ^{2,3}		Low Density Lipoprotein ^{2,3}
lycerides ^{2,3}	Gan	nma-glutamyl	Creatine kina (CK) ⁴	se	
	cium lycerides ^{2,3}	cium Alka pho lycerides ^{2,3} Gar tran	sium Alkaline phosphatase	Alkaline phosphatase lycerides ^{2,3} Glutamic- Oxaloacetic Transaminase (SGOT) Alanine Aminotransfe (ALT)/ Serun Glutamic-Pyre Transaminase (SGPT) Cholesterol ^{2,3} Creatine kina (CK) ⁴	atinine Sodium Alanine atinine Sodium Alanine Aminotransferase (ALT)/ Serum Glutamic-Oxaloacetic Transaminase (ALT)/ Serum Glutamic-Pyruvic Transaminase (SGPT) cium Alkaline phosphatase Cholesterol ^{2,3} lycerides ^{2,3} Gamma-glutamyl transferase (GGT) ⁴ Creatine kinase

• pH, glucose, protein, blood, ketones, by dipstick

• Microscopic examination (if blood or protein is abnormal)

Laboratory Assessments

Parameters

Other Clinical Laboratory Tests

- alcohol breath test and urine drug screen (to include at minimum: amphetamines, barbiturates, cocaine, opiates, cannabinoids and benzodiazepines)
- Serology (HIV antibody, hepatitis B surface antigen [HBsAg], and hepatitis C virus antibody)
- Urine cotinine

The results of each test will be loaded electronically into the eCRF.

NOTES:

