8.2. Clinical Laboratory Analyses

Laboratory evaluations will be based on GSK Core Data Standards and will include:

- Hematology laboratory tests
- Chemistry laboratory tests
- Urinalysis
- Liver function tests
- Other screening tests

Clinical laboratory analyses will include all assessments post-baseline. Unscheduled visits will not be included in summary tables and figures, but will be included in listings – see Section 13.4.2.

Details of the planned displays are presented in Appendix 9: List of Data Displays.

The laboratory assessments for each category are displayed below (Table 6 of the protocol):

Laboratory Assessments		Para	meters			
Haematology						
Clotting parameters: APTT PT times Fibrinogen	Platelet Count RBC Count Haemoglobin Haematocrit	RBC Indices: MCV MCH %Reticulocyte	MCV		WBC count with Differential: Neutrophils Lymphocytes Monocytes Eosinophils Basophils	
Clinical Chemis	strv ¹				1	
CRP	Blood Urea Nitrogen (BUN)	Potassium	Aspartate Aminotransfer (AST)/ Serum Glutamic- Oxaloacetic Transaminase (SGOT)		Total and direct bilirubin	
Albumin	Creatinine	Sodium	Alanine Aminotransfer (ALT)/ Serun Glutamic-Pyru Transaminase (SGPT)	1	Total Protein	
Glucose (fasting during Part C ²)	Calcium	Alkaline phosphatase	Cholesterol ^{2,3}		Low Density Lipoprotein ^{2,3}	
High Density Lipoprotein ^{2,3}	Triglycerides ^{2,3}	Gamma- glutamyl	Creatine kinas (CK) ⁴	e		

207546

Laboratory Assessments	Parameters		
	transferase (GGT) ⁴		
Routine Urinaly	vsis		
• Microscopic e	xamination (if blood or protein is a	bnormal)	

- 1. NOTES:
- Details of liver chemistry stopping criteria and required actions and follow-up assessments after liver stopping or monitoring event are given in Section 8.1 and Appendix 7 of the protocol. All events of ALT ≥3 × upper limit of normal (ULN) and bilirubin ≥2 × ULN (>35% direct bilirubin) or ALT ≥3 × ULN and international normalized ratio (INR) >1.5, if INR measured, which may indicate severe liver injury (possible Hy's Law), must be reported as an SAE (excluding studies of hepatic impairment or cirrhosis).
- 2. In Part C at certain time points as per the SoA lipids and glucose samples are required to be taken fasted.
- 3. Screening samples are required to be taken fasted.
- 4. To be analysed at screening, Day-1 and follow up only 1.

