13.9.2. Mock Example Shell Referencing

Table, listing and figure shells will be produced in documents separate to the RAP. These shells will follow the IDSL standards as appropriate and include study specific programming notes to facilitate programming.

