45.	Safety	AE8CP	Part C: Listing of All Adverse Events		SAC
46.	Safety	AE7	Part C: Listing of Subjects Numbers for Individual Adverse Events		SAC
47.	Safety	AE2	Part C: Listing of Relationship Between Adverse Event System Organ Classes, Preferred Terms, and Verbatim Text		SAC
48.	Safety	AE14	Part C: Listing of Reasons for Considering as a Serious Adverse Event		SAC
49.	Safety	AE8CPa	Part C: Listing of Serious Adverse Events		SAC
50.	Safety	AE8CP	Part C: Listing of Adverse Events Leading to Permanent Discontinuation of Study Treatment or Withdrawal from Study		SAC

ICH	CH: Listings							
No.	Population	IDSL / Example Shell	Title	Programming Notes	Deliverable [Priority]			
Lab	oratory							
51.	Safety	LB5	Part C: Listing of All Laboratory Data for Subjects with Any Value Outside of Normal Range or of Potential Clinical Importance		SAC			
52.	Safety	LB5	Part C: Listing of All Laboratory Values Outside of Normal Range or of Potential Clinical Importance		SAC			
53.	Safety	LB14	Part C: Listing of Laboratory Data with Character Results		SAC			
54.	Safety	UR2A	Part C: Listing of Urinalysis Data for Subjects with Any Value of Potential Clinical Importance	PCI is defined as per IDSL - an increase in Protein or Occult Blood post-baseline relative to baseline, or if microscopy is performed.	SAC			
55.	Safety	MH2	Part C: Listing of Medical Conditions for Subjects with Liver Stopping Events		SAC			
56.	Safety	SU2	Part C: Listing of Subtance Use for Subjects with Liver Stopping Events		SAC			
57.	Safety	LIVER6	Part C: Listing of Liver Stopping Event Information for RUCAM Score		SAC			
58.	Safety	LIVER5	Part C: Listing of Liver Monitoring/Stopping Event Reporting		SAC			

ICH: Listings						
No.	Population	IDSL / Example Shell	Title	Programming Notes	Deliverable [Priority]	
ECO	ECG					
59.	Saftey	EG3	Part C: Listing of All ECG Values for Subjects with Any Value of Potential Clinical Importance		SAC	
60.	Safety	EG3	Part C: Listing of ECG Values of Potential Clinical Importance		SAC	
61.	Safety	EG5	Part C: Listing of All ECG Findings for Subjects with an Abnormal ECG Finding		SAC	
62.	Safety	EG5	Part C: Listing of Abnormal ECG Findings		SAC	
Vital Signs						
63.	Safety	VS4	Part C: Listing of All Vital Signs for Subjects with Any Value of Potential Clinical Importance		SAC	
64.	Safety	VS4	Part C: Listing of Vital Signs of Potential Clinical Importance		SAC	

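### The Part C urinalysis flag (SAP Listing 54) has no planned trigger for urinary glucose, which the protocol names as kidney-risk monitoring, and the Part A rule (Listing 21) is not stated

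*SAP*

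**What the plan says.** Urinalysis is one of the three laboratory components of the primary safety endpoint (Protocol 4; SAP 2.2). Protocol 10.4.1 says the primary endpoint will be "presented in tabular and/or graphical format and summarised descriptively according to GSK's Integrated Data Standards Library standards". SAP 8.2 states "Laboratory evaluations will be based on GSK Core Data Standards and will include" and lists urinalysis, referring to Appendix 9 for the displays.

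In Appendix 9 the displays named for urinalysis are Listing 21 (Part A) and Listing 54 (Part C). Both are restricted to participants with a PCI value. The Listing 54 programming note reads "PCI is defined as per IDSL - an increase in Protein or Occult Blood post-baseline relative to baseline", and adds microscopy being performed as a further trigger. Listing 21 has no programming note. SAP 13.9.2 says "Table, listing and figure shells will be produced in documents separate to the RAP".

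In the protocol's risk table (3.3.1), the kidney-function row opens with "Non-adverse increased urinary glucose concentration was seen in female monkeys and rats", and the mitigation column includes "fasting glucose, as well as urinary glucose assessment". The routine urinalysis panel in Protocol Appendix 2 is "pH, glucose, protein, blood, ketones, by dipstick".

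**The concern.** A flagging rule decides whose data a reader of the final report is shown. Here it follows a sponsor default built on protein and blood, while the compound's own risk assessment points to glucose. The protocol gives a reason to look. In the kidney-function row, some rat urinary effects occurred below the maximum predicted human exposure at 45 mg, and the monkey no-effect level was at or below parity with that exposure. Part A doses reached 40 mg (SAP 5.2).

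Blood glucose, which is tabulated, is a different measurement and does not replace a urine result. If the drug caused glucose to appear in urine without a clinically relevant change, the Part C flag would not bring it out. The reader would have to find it in other listings, if it is shown there.

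**Working it through.** No sample-size or error-rate calculation bears on this point. The check is a trace of the rule against the planned procedures, plus counts.

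**1. Can glucose trigger Listing 54?** The stated triggers are:
- an increase in protein: not glucose;
- an increase in occult blood: not glucose;
- microscopy performed: Protocol Appendix 2 limits this to cases where blood or protein is abnormal, so this route leads back to the first two analytes.

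The panel has five analytes (pH, glucose, protein, blood, ketones), of which 2 of 5 can trigger the flag. Appendix 2 also lets the investigator order additional tests, so discretionary microscopy is a conceivable indirect route, but it is not a planned one.

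**2. Is there a urine glucose criterion elsewhere?** SAP 13.7.2 gives PCI criteria and normal ranges for haematology and clinical chemistry only. Its glucose limits (3 and 9 mmol/L) are in the clinical chemistry table. There is no urine criterion.

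**3. Is urinalysis summarised elsewhere?**
- Chemistry tables: 2.9-2.11 and 2.31-2.33 = 6.
- Haematology tables: 2.12-2.14 and 2.34-2.36 = 6.
- Laboratory tables in total: 6 + 6 = 12, of which 0 are urinalysis. None of the 44 safety tables (2.1-2.44) summarises it. The two safety figures are adverse event plots.

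**4. How many participants are involved, at planned enrolment?**
- Part C: subjects were dosed only in Cohorts 4 and 5 (SAP 2.3). Active 10 + 9 = 19, all reported under one 10 mg label (SAP 5.2). Placebo 4 + 9 = 13. Post-dose urinalysis is scheduled on Days 2, 4, 8, 12 and 16 and at follow-up; Day 1 is pre-dose. Both cohorts stopped early, so actual data are fewer.
- Part A, Periods 1-3: six doses (1, 3, 10, 20, 30, 40 mg) with 6 active each = 36 active participant-periods; placebo 6 x 3 = 18.
- Part A, Period 4: 2 x 6 = 12 at 25 mg; placebo 2 x 3 = 6.

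**5. Would Period 4 be comparable with Periods 1-3 in a table?** All 25 mg dosing is in Period 4, with an LPS or GM-CSF challenge. LPS recipients receive saline at 250 mL/hr from 4 h before to 8 h after the challenge: 250 x 12 = 3,000 mL. With LPS expected 0.5 to 2 h after dosing, the infusion runs from 3.5 to 2 h before dosing until 8.5 to 10 h after it. The 6 h urinalysis falls inside that window, so urine may be diluted. Period 4 results should not be set against unchallenged placebo.

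**The case against.** The strongest case against is that the SAP follows the standard the protocol names. A reader might infer from the missing urinalysis table that the SAP breaks the commitment to summarise the primary endpoint. The documents do not support that. Protocol 10.4.1 ties the summary to the sponsor's Integrated Data Standards Library (IDSL), Listing 54 cites the same library, and the library itself is not in the documents. Nor does SAP 8.2 promise one table per item: other screening tests are listed there too, with no summary table.

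A reader might also infer that a urinary glucose signal would be lost. That is too strong:
- Clinically relevant urinalysis changes are recorded as adverse events (Protocol 9.4.7 and Appendix 4) and tabulated by treatment.
- Creatinine, urea nitrogen, electrolytes, albumin and blood glucose appear in the chemistry tables.
- Renal and glycaemic data feed dose-escalation decisions.
- Listings 20 and 53 (character results) carry no PCI restriction in their titles and may show dipstick glucose.
- By its title, Listing 54 covers the urinalysis data of flagged participants, so the glucose results of anyone flagged for protein or blood would presumably be shown.

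Finally, no gap in the rule is shown for Part A. Listing 21's rule is unstated in the SAP and may sit in the separate shells.

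All of this stands, and it narrows the point. The animal glucose finding was also classed as non-adverse. None of it gives glucose a route into the stated Part C flag.

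**Conclusion.** The point holds in a limited form. Under the planned procedures the Listing 54 rule cannot be triggered by urinary glucose, although the protocol names urinary glucose as monitoring for the kidney risk. The corresponding Part A rule is not stated in the SAP. What is missed is an isolated dipstick glucose rise not judged clinically relevant, among at most 19 active and 13 placebo participants in Part C. The effect is on final reporting only.

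The absence of urinalysis tables is a fact, but asking for them is closer to preference than to correcting an error, because groups are small. The conclusion rests on three assumptions: microscopy is done only as the protocol specifies, planned numbers apply without replacements, and the unseen shells do not already add a glucose trigger to Listing 54. The change is worth making because it is specific and nearly free.

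**What to change.** 1. Add any post-baseline increase in dipstick glucose category to the Listing 54 PCI rule.
2. State the PCI rule for Listing 21 in the SAP, and make it the same.
3. Optionally, add one descriptive table for each of Parts A and C counting participants by treatment and worst-case post-baseline dipstick category against baseline, for glucose, protein and blood. In Part A, show Period 4 (12 at 25 mg and its 6 placebo participants) separately from Periods 1-3. In Part C, leave out data collected after each cohort's termination date, as SAP 13.6.1 requires for summaries.

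Items 1 and 2 alone close the flagging gap. The cost is one edited listing rule, one stated rule and, if wanted, two small tables. Urinalysis is already scheduled, so no new data are needed. The downside is a flag that goes beyond the IDSL default and, for the tables, small counts that can be read only descriptively.

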13.9.12. Non-ICH Listings

Part A

r art A						
Non-I	Non-ICH: Listings					
No.	Population	IDSL / Example Shell	Title	Programming Notes	Deliverable [Priority]	
PK						
65.	РК	PK08	Part A: Listing of GSK3358699 Plasma Pharmacokinetic Concentration-time Data		SAC	
66.	РК	PK08	Part A: Listing of GSK3206944 Plasma Pharmacokinetic Concentration-time Data		SAC	
67.	РК	PK08	Part A: Listing of GSK3206944 Intracellular Pharmacokinetic Concentration-time Data		SAC	
68.	РК	PK14	Part A: Listing of Derived GSK3358699 Plasma Pharmacokinetic Parameters		SAC	
69.	РК	PK14	Part A: Listing of Derived GSK3206944 Plasma Pharmacokinetic Parameters		SAC	
Bioma	Biomarkers: Soluble Inflammatory Mediators					
70.	Safety	[Non standard] BIO_L1	Part A: Listing of Absolute Values Percentage Inhibition and Predicted Percentage Inhibition of Soluble Inflammatory Mediators in Blood After Ex-Vivo LPS Activation	S4	SAC	

Part C

Non-ICH	Non-ICH: Listings				
No.	Population	IDSL / Example Shell	Title	Programming Notes	Deliverable [Priority]
PK					
71.	РК	PK07	Part C: Listing of GSK3358699 Plasma Pharmacokinetic Concentration-time Data		SAC
72.	РК	PK07	Part C: Listing of GSK3206944 Plasma Pharmacokinetic Concentration-time Data		SAC
73.	РК	PK07	Part C: Listing of GSK3206944 Intracellular Pharmacokinetic Concentration-time Data		SAC
74.	РК	PK13	Part C: Listing of Derived GSK3358699 Plasma Pharmacokinetic Parameters		SAC
75.	РК	PK13	Part C: Listing of Derived GSK3206944 Plasma Pharmacokinetic Parameters		SAC
Biomark	ers: Soluble Infla	mmatory Med	liators		
76.	Safety	[Non standard] BIO_L1	Part C: Listing of Absolute Values, Percentage Inhibition and Predicted Percentage Inhibition of Soluble Inflammatory Mediators in Blood After Ex-Vivo LPS Activation	S4	SAC

Signature Page for 207546 TMF-1817519 v1.0

Reason for signing: Approved	Name: PPD Role: Approver Date of signature: 22-Jun-2020 11:39:29 GMT+0000
Reason for signing: Approved	Name: PPD Role: Approver Date of signature: 22-Jun-2020 16:34:51 GMT+0000

Signature Page for TMF-1817519 v1.0
